3.1.2. Secondary

- Amenorrhea up to Weeks 24 and 52.
- Time to amenorrhea up to Weeks 24 and 52.

- Time to reduced menstrual blood loss (i.e. ≤ 80 mL and $\geq 50\%$ reduction from baseline) up to Weeks 24 and 52.
- Number of days of uterine bleeding for each 28-day interval up to Week 52.
- Hemoglobin levels at Weeks 12, 24, 36, 52 and 64.

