5.1.2. Number of subjects

It is planned to randomize five hundred (500) subjects in a 1:1:1:1:1 ratio in order to obtain the following initial treatment allocation:

- Placebo OBE2109 + Placebo E2/NETA 100 subjects
- OBE2109 100 mg + Placebo E2/NETA 100 subjects
- OBE2109 100 mg + E2 1 mg/NETA 0.5 mg 100 subjects
- OBE2109 200 mg + Placebo E2/NETA 100 subjects
- OBE2109 200 mg + E2 1 mg/NETA 0.5 mg 100 subjects

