9.3. RANDOMIZATION

A computer - generated random list using the stratification method and created by FlexRandomizer software (Cytel Inc., Boston, MA, USA) will be used for randomization. Allocation of treatment will be performed via a centralized IWRS system. Subjects will be randomized to one of five treatment groups in a 1:1:1:1:1 ratio for OBE2109 placebo, OBE2109 100 mg without add-back, 100 mg with add-back, OBE2109 200 mg without add-back and OBE2109 200 mg with add-back, stratified by race in order to ensure an equal representation of black women between treatment groups.

Subjects will be randomized into blocks of a pre-determined length.

At Week 24 visit, half of the subjects from the Placebo OBE2109 + Placebo E2/NETA arm will be switched to OBE2109 200 mg with add-back (E2 1 mg/NETA 0.5 mg) while the other half will remain on placebo. This allocation will be determined as part of the randomization at Randomization Call (R) and treatment will be continued up to Week 52.

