9.5.3. Secondary Efficacy Analysis

The endpoints amenorrhea, time to amenorrhea, menstrual blood loss and time to reduced menstrual blood loss will be assessed using data up to Week 24 and again using all data up to Week 52. For the subjects on the placebo arm who were randomized to switch treatment to OBE2019 at Week 24, only data up to the time they switch treatment will be used.

The analysis of amenorrhea will be conducted using the same methods as for the primary endpoint.

A sequential testing procedure will be used within each treatment group. Amenorrhea up to Week 24 vs. placebo will be tested at the 0.0125 significance level only if the primary endpoint hypothesis test is rejected, and in the same way, time to amenorrhea up to Week 24 will only be tested (at 0.0125) if the amenorrhea hypothesis test is rejected (see also the ordering of the sequential testing procedure described in section 9.5). The additional efficacy endpoints will be tested at the 0.0125 with no further adjustments for multiplicity.

Time to amenorrhea is defined as the number of days from first dose to the first day for which the subject does not have bleeding (see Section 6.3.1.2) for at least 35 days. Time to amenorrhea will be analyzed using Kaplan-Meier methodology (estimates and plots will be produced) and each OBE2109 group vs. placebo will be compared using a two-sided log-rank test stratified by race. In addition, the treatment difference as measured by the Hazard Ratio and its corresponding 95% Confidence Interval will be estimated using a stratified Cox regression model with race as stratification factor. Time to reduced menstrual blood loss (as defined by the primary endpoint) will be analysed in the same way.

For the 24-Week analysis, subjects who do not have any amenorrhea within the 24-Week period from Study Day 1 up to Week 24 visit will be considered as right-censored data. The date of the last alkaline hematin method assessment reported from Study Day 1 up to the Week 24 visit will be used as time of censoring. Data from the "last alkaline hematin method assessment" form of external data will be used. If no alkaline hematin method assessment is performed after Study Day 1, the date of Study Day 1 will be used as time of censoring.

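### Amenorrhea up to Week 52, tested as a proportion, gives half the placebo arm 24 weeks to qualify and the active arms 52, which biases the comparison toward the drug

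*Protocol*

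**What the plan says.** - **Endpoint.** Protocol Section 3.1.2 lists "Amenorrhea up to Weeks 24 and 52" as a secondary endpoint. Section 2.1.2 puts the incidence of amenorrhea among the objectives for which superiority is to be shown.
- **Definition.** Section 6.3.1.2 asks for a stretch of at least 35 days with no sanitary material returned or a volume below the quantification limit. It is judged on data to Week 24 and again on all data to Week 52.
- **Switch.** Section 9.3 moves "half of the subjects from the Placebo OBE2109 + Placebo E2/NETA arm" to OBE2109 200 mg with add-back at Week 24. Who switches is already settled at randomisation. Section 5.1.2 plans 100 women per arm, so about 50 placebo women switch.
- **Data cut.** Section 9.5.3 covers amenorrhea, time to amenorrhea, menstrual blood loss and time to reduced blood loss together. For the placebo women "who were randomized to switch treatment to OBE2019 at Week 24, only data up to the time they switch treatment will be used".
- **Method.** The same section states: "The analysis of amenorrhea will be conducted using the same methods as for the primary endpoint". By Section 9.5.2 that is a race-stratified CMH test of proportions in the Full Analysis Set, with an odds ratio and a difference in percentages. Time to amenorrhea gets Kaplan-Meier estimates, a stratified log-rank test and a stratified Cox model.
- **Level.** The six endpoints in the sequential procedure of Section 9.5 are all Week 24 endpoints. Additional efficacy endpoints are tested at 0.0125 without further adjustment.

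**The concern.** One data-cut rule serves two kinds of analysis. In a time-to-event analysis a woman whose data stop at Week 24 is censored and contributes what she has. A proportion has no censoring. She stays in the denominator, and unless she had already qualified she counts as not amenorrheic, although 28 of the 52 weeks were never open to her.

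With a cumulative endpoint, cutting follow-up can only remove events, and here it removes them from placebo alone. All four Week 52 contrasts would then favour the drug even if it did nothing. These are estimates for a named secondary endpoint and would be reported as Week 52 efficacy.

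**Working it through.** **The plan's own figure.** The protocol gives no rate or power for Week 52 amenorrhea. Its one sample-size figure, 64 per arm in Section 9.2, concerns the primary endpoint (30% vs 70%, alpha 0.0125, at least 90% power for all four comparisons). It reproduces: with a continuity correction and 0.90^(1/4) = 0.974 power per comparison the formula gives 63. Exact Fisher power at 64 is 0.975 per comparison, that is 0.975^4 = 0.904 for all four if independent. This point does not touch it.

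**Inputs from the protocol.** 100 women per arm; half of placebo cut at Week 24 (day 168); the others and the active arms followed to Week 52 (day 364); a qualifying run of 35 days; alpha 0.0125 two-sided.

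**Assumptions.** Week 24 placebo incidence p24 of 5%, 10% or 20%; a constant rate of entering amenorrhea; no drug effect. A run must start by day 168 − 35 = 133 to be complete by Week 24, and by day 364 − 35 = 329 to be complete by Week 52.

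**Formulas.**
- True 52-week incidence: p52 = 1 − (1 − p24)^(329/133), exponent 2.474.
- Placebo proportion as analysed: m = (p24 + p52)/2.
- Spurious difference: p52 − m = (p52 − p24)/2.

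For p24 = 10%: p52 = 1 − 0.90^2.474 = 22.9%; m = (10 + 22.9)/2 = 16.5%; difference about 6.5 points.

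Type I error is by exact enumeration of the chi-square test in its CMH form with a single stratum: 100 active women at p52 against 50 placebo women at p24 plus 50 at p52.

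| p24 | Active (p52) | Placebo as analysed (m) | Spurious difference | Odds ratio | Type I error (nominal 0.0125) |
|---|---|---|---|---|---|
| 5% | 11.9% | 8.5% | 3.5 points | 1.46 | 0.042 |
| 10% | 22.9% | 16.5% | 6.5 points | 1.51 | 0.084 |
| 20% | 42.4% | 31.2% | 11.2 points | 1.62 | 0.189 |

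**Sensitivity, same three incidences.**
- Ignoring the 35-day run (exponent 364/168 = 2.167): 2.8, 5.2 and 9.2 points; type I error 0.031, 0.059 and 0.126.
- Rate halved after Week 24: 1.8, 3.4 and 6.1 points; type I error 0.019, 0.033 and 0.058.

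**The remedies under no drug effect.**
- CMH against the 50 non-switchers only: no spurious difference; type I error 0.011 to 0.013.
- Log-rank test with switchers censored (20,000 simulated trials for each p24 from 5% to 30%): 0.011 to 0.013.

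**Power of the restricted CMH** (100 vs 50, placebo 22.9% by Week 52):
- Active 40%: pooled proportion (40 + 11.5)/150 = 0.343; null SE √(0.343 × 0.657 × 0.03) = 0.0822; alternative SE √(0.40 × 0.60/100 + 0.229 × 0.771/50) = 0.0770; z = (0.171 − 2.498 × 0.0822)/0.0770 = −0.45; power about 33%.
- Active 60%: the same steps give about 98%.

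**The case against.** **It is a gap in specification, not a wrong rule.** Section 9.5.3 says which data are used; it does not say that switchers count as Week 52 failures. The missing-data rule in Section 9.5.5 is written around Week 24 and does not address planned switchers, and further detail is left to the SAP, which is not at hand. This stands in part. But the protocol itself fixes the data cut, the endpoint, the test and an analysis set that excludes no switchers. Followed as written, they give unequal follow-up.

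**A sound Week 52 analysis is already planned.** Kaplan-Meier, log-rank and Cox analyses of time to amenorrhea run to Week 52 with the same cut. This stands, and it makes the repair cheap. It does not correct the proportion reported beside them.

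**The direction depends on the reading.** Section 9.5.5 could suggest amenorrhea as status in the last available interval. Week 24 status on placebo would then be set against Week 52 status on drug: still not like with like, but not certain to favour the drug. Section 6.3.1.2 and the first-occurrence definition of time to amenorrhea support the cumulative reading.

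**Stronger conclusions a reader might draw, which the protocol does not support.**
- That the formal efficacy claims are compromised. Every endpoint in the hierarchy is read at Week 24, before any placebo woman switches.
- That the 28-day responder intervals after Week 24 share the bias. They are not cumulative; switchers simply have no usable data there, and no error is shown.
- That restricting the comparator costs almost no power. That would borrow 30% vs 70%, which Section 9.2 assumes for reduced blood loss, not for amenorrhea.

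**Conclusion.** The point holds for one analysis: the CMH comparison of amenorrhea up to Week 52. Under the cumulative definition its direction is toward the drug. Its size cannot be fixed from the protocol, which states no placebo amenorrhea rate; the range of about 3 to 11 points rests on the assumed 5% to 20% incidence and a constant rate, and falls to about 2 to 6 points if the rate halves after Week 24. Type I error exceeds 0.0125 in every scenario examined. The log-rank and Cox analyses are sound on this point because the switch is fixed at randomisation, so censoring there does not depend on outcome. It should be corrected before the Week 52 analysis, but it is not a condition for the formal claims.

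**What to change.** Separate the rule for the Week 52 proportion from the rule for time to event, in one of two ways.

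1. **Preferred.** Report the difference in Kaplan-Meier cumulative incidence of amenorrhea at Week 52, with switchers censored at the switch. The estimates are already planned and all placebo women contribute. State the censoring day explicitly: events are dated at the start of the 35-day run, and the check above censored switchers at day 133, the last day on which a complete run could begin before the switch.
2. **Alternative.** Keep the CMH test but restrict the Week 52 placebo comparator to the roughly 50 women randomised to stay on placebo. The comparison remains randomised because the split is made at randomisation.

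The cost is wording in the protocol or SAP. The first option changes the form of the summary from a CMH odds ratio to a difference in cumulative incidence. The second loses precision: power is about 33% for 40% vs 23% and about 98% for 60% vs 23% (assumed rates, 100 vs 50, alpha 0.0125). Under either, the text should say that the Week 24 analysis of amenorrhea keeps the whole placebo arm.

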2.1.2. Secondary

To demonstrate the superior efficacy of OBE2109 alone and in combination with add-back therapy versus placebo on:

- Incidence of amenorrhea.
- Time to amenorrhea.
- Hemoglobin levels.
- Menstrual bleeding.

To evaluate the effect of OBE2109 alone and in combination with add-back therapy versus placebo on:

- Pain.
- Uterine fibroid symptom severity and health-related quality of life.
- Uterus volume.
- Myoma volume.

To evaluate the impact of submucosal fibroids (baseline FIGO classification of 0, 1 or 2) on the primary efficacy endpoint.

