3.1.3. Additional Secondary endpoints

- Pain measured with a numeric rating scale at Weeks 12, 24, 36, 52 and 64.
- Actual blood loss (in mL) for each 28-day interval up to Week 52.
- Reduced menstrual blood loss for each 28-day interval up to Week 52.
- Symptom severity score (UFS QoL) at Weeks 12, 24, 36, 52 and 64.
- Health-related questionnaire (UFS QoL) score at Weeks 12, 24, 36, 52 and 64.
- Quality of life measured with the EQ-5D questionnaire at Weeks 12, 24, 36, 52 and 64.
- Patient Global Impression of Improvement Scale (PGI-I) at Weeks 12, 24, 36, 52 and 64.
- Myoma volume at Weeks 12, 24, 36, 52 and 64.
- Uterus Volume at Weeks 12, 24, 36, 52 and 64.
- Impact of submucosal fibroids (baseline FIGO classification of 0, 1 or 2) on the primary efficacy endpoint.

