9.5.2. Primary Efficacy Analysis

The primary analysis set for the efficacy analyses will be the Full Analysis Set.

The primary analyses of reduced menstrual blood loss at 24 weeks of treatment (last 28 days prior to week 24 visit) will be analysed as a categorical variable (yes / no response) and will be conducted as follows:

Cochran-Mantel-Haenszel (CMH) tests with adjustment for the stratification factor race will be used to test the null hypothesis of no treatment effect for each OBE2109 group vs. placebo with regards to the

proportion of subjects with a reduced menstrual blood loss at 24 weeks. The odds ratios will be estimated from the CMH test together with the associated 95% CI and corresponding p-values. The proportion per treatment arm will be displayed together with exact Clopper-Pearson 95% CIs. The differences in percentages with corresponding 95% Newcombe-Wilson confidence intervals will also be presented. The homogeneity of the odds ratios will be explored using the Breslow-Day test.

In addition to the CMH tests and to further explore a possible interaction between race and treatment, a logistic regression model with terms for treatment, stratification factor race and the interaction between treatment and race will be fitted to the binary response data. Contrast and estimate statements will provide separated tests for each OBE2109 group vs. placebo for each strata. In case of too many empty cells or non-convergence of the model, separated Fisher's exact tests will be used for each comparison versus placebo, within strata. Subjects who discontinue prematurely due to lack of efficacy or adverse events, or who undergo operative or radiological interventions for uterine fibroids, will be considered as non-responders.

In order to account for multiplicity given four different OBE2109 treatment groups, each primary endpoint comparison versus placebo will be conducted at the 0.0125 level of significance, i.e. 0.05 divided by 4.

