In general, between group comparisons for continuous endpoints will be analyzed via repeated measures analysis of covariance, including the baseline and stratification factor race as a covariate, with each treatment group compared versus placebo using contrasts.

Mean hemoglobin will be compared between treatment groups and categorical analyses may also be performed.

Fibroid volume and uterine volume are expected to be log-normally distributed and so will be logtransformed prior to analysis, with the subsequent results (mean differences and corresponding confidence intervals) back transformed and hence reported in terms of ratios. The underlying distributions will be checked, and if deemed necessary alternative analyses may also be conducted. The number of days of uterine bleeding (assessed via the alkaline hematin method) will be analyzed using a negative binomial model or zero-inflated negative binomial, depending on model fit. The PGI-I will be analysed using Mantel-Haenszel methodology.

In order to explore the impact of submucosal fibroids on the efficacy of OBE2109, an analysis of the primary efficacy endpoint will be performed on the subset of patients from the FAS analysis set with a baseline FIGO classification of 0, 1 or 2 in either one fibroid only or in any fibroid, depending on the number of available fibroid data.

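### The analysis planned for the submucosal-fibroid objective covers only women with FIGO 0–2 fibroids and has no contrast with women without them

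*Protocol*

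**What the plan says.** The Synopsis and section 2.1.2 state the objective: "To evaluate the impact of submucosal fibroids (baseline FIGO classification of 0, 1 or 2) on the primary efficacy endpoint". Section 3.1.3 repeats it among the additional secondary endpoints.

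The statistical part of the Synopsis says only that this impact will be evaluated. Section 9.5.3 gives the method. Its purpose is stated as "In order to explore the impact of submucosal fibroids on the efficacy of OBE2109", and the means is that "an analysis of the primary efficacy endpoint will be performed on the subset of patients from the FAS analysis set" with baseline FIGO class 0, 1 or 2, counted "in either one fibroid only or in any fibroid, depending on the number of available fibroid data". The protocol describes no analysis of women without such fibroids, no treatment-by-FIGO term and no comparison between the two groups.

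Race is handled differently. Section 9.5.2 specifies "a logistic regression model with terms for treatment, stratification factor race and the interaction between treatment and race", with contrasts against placebo in each stratum, and adds: "The homogeneity of the odds ratios will be explored using the Breslow-Day test".

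The submucosal question is not among the six steps of the sequential procedure in section 9.5. The same section says that additional efficacy endpoints are tested at 0.0125 without further adjustment.

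**The concern.** The impact of a baseline feature on the efficacy of a drug is a comparison: the effect against placebo in women who have the feature, set against the effect in women who do not. Section 9.5.3 plans only the first half. It answers whether the drug works in women with submucosal fibroids, which is a sensible question but not the one in sections 2.1.2 and 3.1.3.

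The p-value from the subset does not fill the gap. A significant result does not show that submucosal fibroids make no difference, and a non-significant one may reflect small numbers. What is at stake is whether a named objective receives a formal estimate. No confirmatory claim depends on it.

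**Working it through.** **Inputs from the protocol.** Response 30% on placebo and 70% on active (section 9.2); 0.0125 per comparison (sections 9.2 and 9.5), two-sided (section 9.5); 100 women per arm (section 5.1.2); randomization stratified by race only (section 9.3).

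**Assumptions.** The protocol gives no share of women with submucosal fibroids, so 10% to 50% is used. For effect modification, the effect in the subset is taken as half that in the other women: 30% vs 50% against 30% vs 70%. Race strata are ignored.

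**The plan's own figure.** Section 9.2 states 64 per group for at least 90% power to reject all four comparisons. The two-proportion formula with continuity correction, two-sided 0.0125 and 97.5% power per comparison (1 − 0.10/4) gives 63. Exact joint power at 64 per arm with a shared placebo group is 94.5% (chi-square) or 92.2% (Fisher). The inputs are therefore read as the protocol meant them. The point does not depend on this figure.

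**Step 1: what the subset result leaves open.** Interaction = subset difference − difference in the other women. With a 30% share and a subset difference of 25 points:

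| Difference in other women | Overall difference | Interaction |
|---|---|---|
| 25 points | 0.3×25 + 0.7×25 = 25.0 | 0 |
| 40 points | 0.3×25 + 0.7×40 = 35.5 | −15 |
| 55 points | 0.3×25 + 0.7×55 = 46.0 | −30 |

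The subset estimate is the same in all three rows. Only the data outside the subset tell them apart.

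**Step 2: what the subset p-value tells.** With n submucosal women per arm, p̄ the mean of the two rates and z = 2.498 for two-sided 0.0125:

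power = Φ{[d − z√(2p̄(1−p̄)/n)] / √[(p₁(1−p₁) + p₂(1−p₂))/n]}

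For n = 30 and 30% vs 70%: (0.40 − 2.498×0.1291)/0.1183 = 0.655, so power is 74%.

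| Submucosal women per arm | 10 | 20 | 30 | 40 | 50 |
|---|---|---|---|---|---|
| No modification (30% vs 70%) | 22% | 51% | 74% | 88% | 95% |
| Effect halved (30% vs 50%) | 5% | 11% | 18% | 25% | 32% |

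Subset significance follows the size of the subset as well as the effect in it.

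**Step 3: what the missing contrast could deliver.** For one active arm against placebo, with share s, the true difference between the two effects is 20 points and

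SE = √[0.21/(100s) + 0.25/(100s) + 0.21/(100(1−s)) + 0.21/(100(1−s))], power = Φ(0.20/SE − 1.960) at two-sided 0.05.

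For s = 0.3: SE = √(0.0070 + 0.0083 + 0.0030 + 0.0030) = 0.146, and Φ(1.369 − 1.960) = 28%.

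| Submucosal share | 10% | 20% | 30% | 40% | 50% |
|---|---|---|---|---|---|
| SE, points | 22.5 | 16.8 | 14.6 | 13.6 | 13.3 |
| Power at 0.05 | 14% | 22% | 28% | 31% | 33% |
| Power at 0.0125 | 5% | 10% | 13% | 15% | 16% |
| Power at 0.05, four active arms pooled | 21% | 34% | 42% | 47% | 49% |

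The logistic model works on the log-odds scale, where the answer is similar. For s = 0.3 the difference in log odds ratios is ln(7/3) = 0.847 and SE = √(1/6.3 + 1/7.5 + 1/14.7 + 1/14.7) = 0.654, so power is Φ(1.295 − 1.960) = 25%. At a 30% share the 95% interval for the interaction is about ±1.96×14.6 = ±29 points for one arm.

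**The case against.** The strongest reply is that section 9.5.3 promises an analysis in the subset without saying it is the only one, and that section 9.5 leaves further detail to a statistical analysis plan, which is not among the documents at hand. That plan may add the contrast. But section 9.5.3 states both a purpose and a population, and the two do not match. A plan that follows the protocol as written inherits the gap.

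A second reply is that the primary analysis covers the whole Full Analysis Set, so subtracting subset counts from overall counts gives the response rates in the other women. That is correct. A reader might infer from section 9.5.3 that these women are never looked at, or that the objective is beyond reach with this trial's data; the documents do not support either. What is missing is a planned contrast with a confidence interval.

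Third, race is the stratification factor and part of the primary test, so its fuller treatment is natural. This stands. The comparison shows only that a suitable method is already in the protocol.

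Fourth, the open subset definition might be read as a choice made after seeing results. The text ties it to how much fibroid data is available, not to outcomes, and it can be settled blind. It is a loose end, not evidence of selection.

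Finally, the interaction test is itself weak, so low subset power is no argument for it. The argument rests on the mismatch between question and analysis.

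**Conclusion.** The point holds in a limited form. The analysis in section 9.5.3 gives the treatment effect in women with FIGO 0–2 fibroids but not whether submucosal status changes that effect, which is the question set in sections 2.1.2 and 3.1.3. Step 1 shows this without assuming any particular prevalence: the subset figure alone is compatible with no modification or with a large one.

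The consequence is modest. The item is exploratory, an additional secondary endpoint outside the sequential procedure, so the primary conclusion, type I error control and sample size are untouched.

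A reader might turn one minus the subset power into a rate of wrongly declaring a lost effect. The documents do not support that. The protocol plans no such inference from a non-significant subset result, and it gives no submucosal share. Over an assumed 10–50% share, subset power at 0.0125 with no effect modification runs from about 22% to 95%, so no single figure can be defended.

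**What to change.** Replace the subset-only sentence in section 9.5.3, or supplement it in the statistical analysis plan before the Week 24 unblinding, as follows.

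- In the whole Full Analysis Set, fit a logistic model for the primary endpoint with treatment, race, baseline submucosal status and the treatment-by-submucosal interaction.
- For women with and without submucosal fibroids, report response rates by arm and differences from placebo with confidence intervals.
- Report the interaction estimate with its confidence interval for each active arm and read it as estimation, since power is low (Step 3).
- Fix one definition of submucosal status from baseline data. Any FIGO 0–2 fibroid is the natural choice if FIGO type is recorded for all measured fibroids. This needs checking: section 6.3.5 requires dimensions of the three largest myomas, and the screening ultrasound list in section 6.2.1 does not mention recording FIGO type. If it is not recorded for all, state the alternative definition now.

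The cost is one extra model and one table. No new data are needed if baseline FIGO type is already captured as above.
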